7.1.2 Level of Significance

A two-sided alpha level of 0.05 will be used for all comparisons.

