7.2 Primary Analysis

7.2.1 Primary Endpoint Analysis

Objective: To compare diagnostic performance (accuracy, sensitivity, specificity, PPV, NPV) across the three study conditions.

Diagnostic Performance Metrics:

For each reader and condition, the following metrics will be calculated:

- **Accuracy:** Overall proportion of correct diagnoses
- **Balanced Accuracy:** Average of sensitivity and specificity, accounting for class imbalance
- **Sensitivity:** Proportion of APL cases correctly identified
- **Specificity:** Proportion of non-APL cases correctly identified
- **Positive Predictive Value (PPV):** Proportion of APL predictions that are correct
- **Negative Predictive Value (NPV):** Proportion of non-APL predictions that are correct
- **Weighted F1 Score:** Harmonic mean of precision and recall, weighted by class prevalence

Statistical Method: Friedman test (a non-parametric test for repeated measures across multiple groups) followed by a Wilcoxon signed-rank test.

Rationale: The Friedman test is the appropriate statistical method for this study design because:

- **Within-subject design:** Each reader evaluates cases under all three conditions, creating paired data
- **Non-parametric approach:** Does not assume normal distribution of performance metrics, which is appropriate for bounded proportions (0-1 range)
- **Accounts for reader variability:** Controls for baseline differences among readers by treating each reader as a block, focusing on within-reader differences across conditions
- **Multiple conditions:** Simultaneously tests for differences among three related groups (X, Y1, Y2) rather than requiring multiple pairwise tests
- **Robust to outliers:** Uses rank-based methods that are less sensitive to extreme values

Analysis Procedure:

1. **Global test:** For each performance metric, conduct a Friedman test with the null hypothesis that the distributions of the metric are identical across all conditions.
2. **Significance threshold:** Two-sided alpha = 0.05.
3. **Post-hoc pairwise comparisons:** If the Friedman test yields $p < 0.05$ for a given metric, conduct pairwise Wilcoxon signed-rank tests for all condition pairs.

Wilcoxon Signed-Rank Test Rationale: This paired non-parametric test is appropriate for two-sample comparisons because it preserves the within-reader pairing structure and does not assume normality of the differences between conditions.

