7.3.4 Decision-Change Rates

Statistical Method: Series of exact binomial tests to evaluate decision changes and their clinical impact in Condition Y1 (AI-generated predictions shown after participants recorded their initial diagnoses).

Rationale:

- **Distribution-free:** Does not assume normality or large-sample approximations
- **Appropriate for binary outcomes:** Tests proportions of categorical outcomes (changed/unchanged, beneficial/harmful)
- **Exact inference:** Provides exact p-values based on the binomial distribution rather than asymptotic approximations
- **Multiple hypotheses:** Evaluates whether (1) changes occur, (2) changes are beneficial, and (3) overall improvement is achieved

Analysis Procedure:

1. For Condition Y1 only, identify the diagnosis before (Y1_PRE) and after the AI-generated prediction is displayed (Y1_POST).
2. Calculate overall decision-change rate: proportion of all Y1 cases with diagnostic revision.
3. Classify each decision change according to alignment with ground truth:
 - Beneficial (I→C): Incorrect initial diagnosis corrected after viewing AI
 - Harmful (C→I): Correct initial diagnosis changed to incorrect after viewing AI
4. Statistical Testing:
 - Test 1 - Overall Change Rate:
 1. Null hypothesis: Decision change rate = 0 (no changes occur)
 2. Test: One-sided exact binomial test
 3. Evaluates: Whether clinicians revise their diagnoses after viewing AI
 - Test 2 - Direction of Changes (among changes only):
 1. Null hypothesis: The likelihood of beneficial changes = The likelihood of harmful changes
 2. Test: One-sided exact binomial test comparing number of beneficial vs. harmful changes
 3. Evaluates: Whether changes tend to improve or worsen diagnostic accuracy
 - Test 3 - Overall Improvement Rate (all Y1 cases):
 1. Null hypothesis: Improvement rate = 0 (AI provides no benefit)
 2. Test: One-sided exact binomial test
 3. Evaluates: Proportion of all Y1 cases where AI led to correction of an initially incorrect diagnosis

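### Decision-change Tests 1 and 3 take a null rate of exactly zero, so their p-values only report whether any event occurred, and Test 3 leaves out harmful switches

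*Combined protocol and SAP*

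**What the plan says.** Section 7.3.4 (Decision-Change Rates) plans three one-sided exact binomial tests on Condition Y1, comparing each reader's diagnosis before and after the AI call is shown. The series is introduced with this purpose: "Evaluates whether (1) changes occur, (2) changes are beneficial, and (3) overall improvement is achieved".

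- Test 1: "Null hypothesis: Decision change rate = 0 (no changes occur").
- Test 2, among changed decisions only: "One-sided exact binomial test comparing number of beneficial vs. harmful changes". Its stated purpose is "Whether changes tend to improve or worsen diagnostic accuracy". The direction of the one-sided alternative is not given.
- Test 3: "Null hypothesis: Improvement rate = 0 (AI provides no benefit"). Its statistic is "Proportion of all Y1 cases where AI led to correction of an initially incorrect diagnosis".

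Section 7.1.2 sets the general rule: "A two-sided alpha level of 0.05 will be used for all comparisons".

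Three other places bear on the point. Section 6.2.4 plans a net decision-change rate but attaches no test or interval to it. Section 6.2.5 defines net benefit as an accuracy difference between unaided and aided conditions, and Section 7.3 gives no method for it. The aim in Section 7.2.1 is "To compare diagnostic performance (accuracy, sensitivity, specificity, PPV, NPV) across the three study conditions", which compares X, Y1 and Y2 rather than the same reads before and after the AI call.

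**The concern.** An exact binomial test needs a null rate under which the data can vary. At a rate of exactly zero nothing can vary: a single event is impossible under the null, so one event rejects it with certainty and no events never do. The p-values of Tests 1 and 3 therefore repeat whether the count was zero, which the planned rates already show.

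For Test 1 this is uninformative but not misleading, since the conclusion that some diagnoses were changed is literally true after one change. Test 3 is worse, because its null is glossed as the absence of benefit and its rejection is meant to answer whether overall improvement was achieved. Its statistic contains corrections only. Switches from correct to incorrect do not enter, so it can reject its null when accuracy was unchanged or fell. A report could then carry p = 0 against no benefit on data that show net harm.

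Test 2 is the one test in the section that sets benefit against harm. Its one-sided form conflicts with Section 7.1.2 and with its own aim of covering both improvement and worsening.

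**Working it through.** **Denominator.** 10 readers × 102 slides = 1,020 decisions, which reproduces the total in Section 5.3. Condition Y1 has 10 × 34 = 340 reads. The plan gives no expected change rate, power or event count for these tests, so every event count below is an assumption.

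**Tests 1 and 3.** The p-value is P(K ≥ k) for K ~ Binomial(340, 0). All the probability sits at K = 0, so:

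- k = 0: p = 1
- k = 1, 2, 5 or 20: p = 0

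The two-sided version gives the same values for k = 0, 1, 2 and 5. No choice of alpha changes the decision.

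The estimate says much more than the p-value. One correction in 340 is 0.29%, with exact 95% interval 0.01% to 1.63%. None in 340 leaves rates up to 1.08% inside the interval. Both intervals treat reads as independent.

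**Chance that Test 3 rejects** at a true correction rate r, again with independent reads: 1 − (1 − r)^340.

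| r | P(reject) |
|---|---|
| 0.1% | 29% |
| 0.5% | 82% |
| 1% | 97% |
| 2% | 99.9% |

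The rate of harmful switches does not appear in this formula.

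**Omitted harm and sidedness.** Let b be beneficial and h harmful changes. Net change = (b − h)/340. Test 2 refers b to Binomial(b + h, 0.5).

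| b | h | Net change (points) | Test 3 p | Test 2 towards benefit | Test 2 towards harm | Test 2 two-sided |
|---|---|---|---|---|---|---|
| 1 | 9 | −2.35 | 0 | 0.999 | 0.011 | 0.021 |
| 5 | 5 | 0 | 0 | 0.623 | 0.623 | 1.00 |
| 5 | 15 | −2.94 | 0 | 0.994 | 0.021 | 0.041 |
| 10 | 2 | +2.35 | 0 | 0.019 | 0.997 | 0.039 |

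For the first row: (1 − 9)/340 = −2.35 points; towards benefit 1023/1024 = 0.999; towards harm 11/1024 = 0.011; two-sided 22/1024 = 0.021.

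Test 3 returns the same p-value whether accuracy rose, stayed level or fell. Test 2 separates these cases, but what the planned one-sided version would report depends on a direction that the plan does not state.

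**The case against.** The strongest reply is that nobody would read Test 3 alone. The same section classifies each change as beneficial or harmful and compares the two in Test 2. Section 6.2.4 reports a net rate and the share of changes that helped, Section 6.2.5 plans an accuracy difference, and Section 7.2.1 tests accuracy between conditions. In the 1-versus-9 example these outputs would show the counts and the net fall of 2.35 points. Section 2.2 also frames this objective as quantification. All of that stands, and it limits the damage. It does not repair Test 3, whose label and stated purpose remain wrong. Nor does any planned test give a two-sided answer, net of harm, on the same reads before and after the AI call, although Y1 records exactly those pairs.

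Two stronger readings are tempting and are not supported.

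- *Test 2 cannot show worsening.* This holds only if the alternative is benefit. The plan does not say so, and directed at harm the same example gives p = 0.011. What can be said is that the direction is missing and that one-sidedness conflicts with Section 7.1.2.
- *Test 3 will often reject while accuracy falls.* How often depends on AI accuracy, readers' initial accuracy and switching rates, none of which the documents give. A simple model also has to assume independent reads, and equal AI accuracy and equal switching on initially right and wrong reads. Under it the probability runs from below 0.1% (AI accuracy 98%) to over 99% (50%), both at 85% initial accuracy and 20% switching on disagreements. No frequency should be claimed.

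**Conclusion.** The point holds for Tests 1 and 3 as written. That their p-values can only be 0 or 1 follows from the zero null and needs no assumption about the data. That Test 3 cannot establish overall improvement follows from its statistic; the 1-versus-9 counts only illustrate it. The mismatch between Test 2 and Section 7.1.2 is a smaller, separate inconsistency.

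The reach is narrow. One secondary objective is affected, and the planned net rate, Test 2 and the between-condition accuracy comparisons partly contain the problem. A reader might infer that the trial's main conclusion on AI assistance is compromised. It is not: the Friedman and Wilcoxon analysis in Section 7.2.1 does not use these tests. This should be fixed before the decision-change results are reported, and it rates no higher than that.

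**What to change.** - Drop the p-values for Tests 1 and 3.
- Report the rates of any change, of beneficial change, of harmful change and of net change (beneficial minus harmful) over the 340 reads, each with a 95% confidence interval that allows for shared readers and slides, for example from a bootstrap that resamples both. Slides matter because all readers draw on the same 102 slides (Section 3.4), each with one fixed binary AI call (Section 3.6). On average 340/102 = 3.3 readers see a slide in Y1, and switches towards the AI on one slide all go the same way.
- If a category has no events, a bootstrap interval collapses to zero width. Give the exact binomial interval instead and state that it assumes independent reads.
- Judge net improvement two-sided, from the net-rate interval.
- Make Test 2 two-sided, which is the exact McNemar test, and state that it assumes independent reads.
- Label all of this as post hoc. Section 10.2 gives completion as October 10, 2025, and Section 10.3 records no amendments.

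The cost is some SAP wording and a few lines of code on data already captured. Two uninformative p-values disappear, and significance for benefit becomes harder to reach. In Test 2, five beneficial and no harmful changes give p = 0.031 one-sided towards benefit but 0.063 two-sided. The two-way interval is more demanding still. Six illustrative simulated scenarios assumed 5 to 20 contested slides, 30% to 80% of Y1 reads on them switching towards the AI, and the AI right on 90% of them. The interval excluded zero in 16% to 82% of runs, against 61% to 98% rejection for two-sided Test 2. That comparison is not like for like: with the AI right on half of the contested slides, so no net effect over slides, Test 2 rejected in 10% to 26% of runs and the interval in 1% to 4%. These ranges depend on the assumed scenarios, and the documents supply none of the inputs.

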7.3.5 Diagnostic Confidence

Objective: To assess whether AI assistance affects clinician confidence in their diagnoses, particularly in Condition Y1 where pre-AI and post-AI confidence can be compared.

7.3.5.1 Overall Distribution Comparison

Statistical Method: Wilcoxon signed-rank test.

Rationale:

- **Paired data:** Compares pre-AI and post-AI confidence for the same clinician on the same slide, preserving the within-subject pairing structure

- **Ordinal data:** Confidence ratings (1-5 scale) are ordinal in nature; Wilcoxon uses rank-based methods that appropriately handle ordinal measurements without assuming interval properties or normal distributions
- **Non-parametric approach:** Does not require assumptions about the underlying distribution of confidence scores
- **Sensitive to magnitude:** Considers both the direction and magnitude of changes in confidence, not just the presence or absence of change

Analysis Procedure:

1. **Data structure:** For each participant-slide pair in Condition Y1, extract the confidence rating before (Y1_PRE) and after (Y1_POST) viewing the AI prediction.
2. **Unit of analysis:** Individual slide-level assessments (participant \times slide pairs), treating each diagnostic decision as an independent paired observation. This slide-level approach directly evaluates confidence changes at the natural unit of measurement (the diagnostic decision).
3. **Global test:** Conduct a Wilcoxon signed-rank test with the null hypothesis that the distribution of confidence scores is identical between Y1_PRE and Y1_POST.
4. **Significance threshold:** Two-sided alpha = 0.05.

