1.5 Study Population

Participants (Readers): Board-certified pathologists and hematologists who routinely perform hematopathology diagnoses. Target enrollment: 10 participants (actual enrollment: 10 participants).

Cases (Pathology Slides): De-identified Wright-Giemsa-stained bone marrow aspirate WSIs with confirmed diagnoses. Each participant reviews 102 slides (34 slides per condition, stratified by APL status).

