3.6 AI System (LEAP) Implementation

The LEAP AI system generates diagnostic predictions independently for all 102 WSIs before the study session begins. During the study:

- **Condition X (Unaided):** AI predictions are not shown to the clinician
- **Condition Y1 (AI as Double-Check):** AI prediction is revealed only after the clinician submits their initial diagnosis
- **Condition Y2 (AI as First Look):** AI prediction is visible throughout the review

AI predictions are presented as binary classifications (APL vs. non-APL).

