7.3.3 Concordance Between AI Predictions and Clinicians' Diagnoses

Statistical Method: Permutation tests comparing AI predictions to clinician decisions.

Rationale:

- **Distribution-free:** Avoids large-sample and normality assumptions by creating an empirical null distribution through random permutations
- **Appropriate for proportion comparison:** Tests whether the proportion of cases where clinicians agree with AI differs significantly between conditions
- **Robust to small samples:** Does not rely on asymptotic approximations
- **Exact p-values:** Provides exact statistical inference rather than relying on theoretical distributions
- **Slide-level analysis:** Treats each clinician's diagnosis on each slide as an independent observation when comparing concordance rates between conditions

Analysis Procedure:

1. For each condition and each slide, determine the AI prediction (APL vs. non-APL).
2. For each clinician's diagnosis, determine whether it matches the AI prediction (concordant vs. discordant).
3. Calculate the overall concordance rate for each condition: proportion of all clinician-slide pairs where the diagnosis matches the AI prediction.
4. Conduct pairwise permutation tests comparing concordance rates between conditions:
 - Calculate the observed difference in concordance rates between two conditions
 - Randomly permute condition assignments while preserving the total number of observations per condition
 - Recalculate the difference in concordance rates for each permutation ($n=10,000$ permutations)
 - Compute two-sided p-value as the proportion of permuted differences as extreme or more extreme than the observed difference

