7.3.5.2 Level-Specific Confidence Changes

Statistical Method: McNemar test for paired pathology evaluation with and without AI.

Rationale: The McNemar test is appropriate because:

- **Paired data:** Compares pre-AI and post-AI confidence for the same clinician on the same cases
- **Binary classification:** At each confidence level (1-5), each case can be classified as either at that confidence level or not
- **Focus on discordant pairs:** Tests whether changes in confidence at a specific level differ significantly between pre-AI and post-AI assessments
- **Accounts for within-subject dependence:** Properly handles the matched nature of pre- and post-AI assessments
- **No distributional assumptions:** Non-parametric test suitable for ordinal confidence ratings

Analysis Procedure:

1. For each confidence level (1 = Random Guess, 2 = Very Doubtful, 3 = Unsure, 4 = Mostly Certain, 5 = Absolutely Certain) in Condition Y1 (AI as Double-Check):

- Create binary indicators: 1 if confidence equals that level, 0 otherwise
- Construct 2×2 contingency table comparing pre-AI vs. post-AI classifications
- Conduct McNemar exact test with null hypothesis that the proportion of cases at that confidence level is unchanged by AI exposure

2. Calculate the proportion of cases at each confidence level before and after AI review
3. Compute the change in proportion (post-AI minus pre-AI) for each confidence level
4. Report both increases and decreases in confidence at each level following AI review.

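### The confidence test in 7.3.5.1 treats 340 reads from 10 readers as independent, so its p-value can be too small for conclusions about clinicians in general

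*Combined protocol and SAP*

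**What the plan says.** Section 7.3.5 gives the aim: "To assess whether AI assistance affects clinician confidence in their diagnoses, particularly in Condition Y1". For the overall comparison, 7.3.5.1 takes every reader-by-slide pair in Condition Y1 and applies a Wilcoxon signed-rank test, two-sided at 0.05, "treating each diagnostic decision as an independent paired observation". Section 7.3.5.2 puts the same reads into one 2×2 table for each of the five confidence levels and applies an exact McNemar test. It claims to deal with within-subject dependence, but explains this as follows: "Properly handles the matched nature of pre- and post-AI assessments". That is the before/after matching, not the 34 reads that share a reader.

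The plan treats readers differently elsewhere. Section 7.2.1 makes the reader the block, and 7.3.1 reduces review times to one median per reader and condition. No reader-level or clustered analysis of confidence is planned. Section 1.5 describes the readers by profession ("Board-certified pathologists and hematologists who routinely perform hematopathology diagnoses"), and nothing limits the confidence conclusions to the 10 who took part.

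On a related point, Test 2 in 7.3.4 is a "One-sided exact binomial test comparing number of beneficial vs. harmful changes", while 7.1.2 says "A two-sided alpha level of 0.05 will be used for all comparisons".

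**The concern.** The signed-rank test works on changes, so a reader who is always confident causes no difficulty. The difficulty is that readers may differ in how strongly they respond to the AI. If so, the 34 changes from one reader resemble each other, and 340 reads carry less information about clinicians than 340 independent changes would. Section 7.3.5 asks about clinician confidence, which reads most naturally as clinicians in general. For that target, differences between readers in the shift are sampling error, and the pooled test leaves them out.

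At stake is a report that AI significantly raises clinician confidence when the result rests on a few strongly responding readers. Nothing planned would reveal this.

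**Working it through.** **Inputs.** 10 readers (4.1.1); 34 Y1 slides per reader (4.2.1); a separate random allocation of the same 102 slides for each reader (3.4); two-sided 0.05 (7.1.2). The plan's total reproduces: 10 × 102 = 1,020 decisions (5.3). The Y1 part is 10 × 34 = 340 reads, or 340/102 ≈ 3.3 per slide. The documents give no ICC, share of unchanged scores or switching rate, so all such values below are assumptions.

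**Formula, readers only.** Design effect D = 1 + (34 − 1) × ICC; effective N = 340/D; actual error ≈ 2 × [1 − Φ(1.96/√D)].

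| Reader ICC of changes | D | Effective N | Error |
|---|---|---|---|
| 0 | 1.00 | 340 | 5.0% |
| 0.02 | 1.66 | 205 | 12.8% |
| 0.05 | 2.65 | 128 | 22.9% |
| 0.10 | 4.30 | 79 | 34.5% |

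**Simulated pooled Wilcoxon error** (readers drawn at random, average shift zero):

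- Changes from −2 to +2, 2,000 runs: 11.9%, 19.6% and 32.0% at observed reader ICC 0.016, 0.042 and 0.083; 4.7% with no clustering.
- With 38%, 79% or 90% of scores unchanged, 4,000 runs per cell: 12.5–13.4% at observed ICC 0.02, 22.4–23.7% at 0.05 and 35.2–36.2% at 0.10. Adding a latent slide ICC of 0.10 gives 15.2–15.5%, 24.3–26.2% and 36.1–37.7%.
- With the five rating levels modelled explicitly: about 20–27% at ICC 0.04–0.075 and 29–33% at 0.08–0.10.
- These 10 readers as the whole target (fixed shifts summing to zero): 3.8–5.3%, or 5.8–7.6% with slide ICC 0.10.

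**McNemar tests.** A reader drifting upward moves some reads from 3 to 4 (into level 4) and others from 4 to 5 (out of it). At middle levels these flows largely cancel. At level 5 upward movement only adds, so the drift remains. With starting shares for levels 1 to 5 of 5/10/20/35/30% or 2/5/13/30/50%, latent change SD 1.0 or 0.4, reader shifts only and 2,000 runs:

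- Observed ICC 0.023–0.054: levels 1–4 reject 1–6%, level 5 6–13%.
- Observed ICC 0.070–0.095: levels 2–4 reject 3–7%, level 1 2–9%, level 5 15–21%.

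A further level-by-level simulation over ICC 0.04–0.10 gave 3–6% at levels 2–4, 1–10% at level 1 and about 9–18% at level 5.

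**Reader-level test.** A signed-rank test on the 10 reader mean changes rejected 4.2–5.2% for latent reader ICC 0 to 0.20 without slide effects. Its smallest two-sided p is 2/2^10 = 0.002, so 0.05 is within reach. Because slides are shared between readers, slide clustering also links the reader means: with slide ICC 0.10 the test rejected 5.4% (latent reader ICC 0.05) and 8.1% (reader ICC 0). A reader-and-slide cluster-robust t test with 9 df, run on the direction of change, gave 3.8–6.1%.

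**Test 2 in 7.3.4.** LEAP gives one fixed binary call per slide (3.6), so switches toward it on one slide are all beneficial or all harmful. Suppose AI is right on half of 8–20 contested slides, and changes per slide follow Bin(10, s/3), where s is the switching rate (6,000 runs). One-sided error is 0.8–3.3% at s = 10%, 4.3–6.7% at 20%, 6.6–8.6% at 30%, 13.5–14.5% at 60% and 17.4–18.4% at 90%. The simulation standard error near 18% is √(0.18 × 0.82/6000) ≈ 0.5 points.

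**The case against.** The strongest reply is that the inflation depends on a target the plan does not state. If AI changes nobody's confidence, or if inference stops at these 10 readers, differences between readers do not inflate the error. The assumption is also stated openly, no ICC is available, and the analyses are secondary with no success rule. All of this stands. It makes the finding conditional, but it does not justify leaving the target unstated when 7.3.5 speaks of clinicians.

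Three stronger readings are tempting, and the documents do not support them.

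- A reader might carry the Wilcoxon figures over to the McNemar tests, because both pool the same reads. The tables in 7.3.5.2 count reads at one level, not all upward against all downward moves, so the effect varies by level and with a starting distribution that the documents do not give. No single McNemar figure is justified.
- A reader might infer that 7.3.3 fails too, since it treats each diagnosis "as an independent observation when comparing concordance rates between conditions". There, slides are randomised to conditions within each reader, so reader and slide main effects do not inflate the test (3.5–4.2% in simulation). It exceeds 5% only if AI's effect on concordance differs between readers.
- A reader might call Test 2 invalid because of slide clustering. At 10–30% switching its one-sided error is only about 1–9%.

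A further fair point is that 7.3.5.1 chose the signed-rank test because it uses the size of a change as well as its direction. A replacement should keep that property, and a test on reader means does.

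**Conclusion.** The point holds for 7.3.5.1 and should be fixed. If the conclusion is about clinicians in general, the nominal 5% test has an actual error of about 12–13%, 20–25% and 30–36% at assumed observed reader ICCs of 0.02, 0.05 and 0.10. With no reader or slide clustering, or for these 10 readers alone, it is near 5% (about 6–8% with slide ICC 0.10). For 7.3.5.2 the concern is weaker: middle levels stay near nominal, and mainly level 5 is inflated, by an amount that depends on the starting distribution.

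This does not show that the reported confidence result is wrong; the real ICC may be negligible and can be computed from the data. The primary and time analyses work at reader level and are not touched.

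The one-sided Test 2 contradicts 7.1.2 whatever the clustering. Clustering matters there only if switching is frequent: about 14–19% one-sided error at 60–90% assumed switching, allowing for simulation error.

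**What to change.** **7.3.5.1.** State the target. For clinicians in general, make the main test a signed-rank or exact sign-flip test on the 10 reader mean changes (post minus pre). Report the reader ICC of the observed changes and label the pooled slide-level p-value descriptive. Add a reader-and-slide cluster-robust sensitivity analysis, because the reader-level test can run at about 5–8% if slides also cluster. Otherwise, limit the conclusion to these 10 readers.

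**7.3.5.2.** Apply the same reader-level test to each reader's change in the proportion of reads at each level, with pooled McNemar p-values as descriptive. At rarely used levels, if only five readers change, the sign-flip test cannot go below 2/2^5 = 0.0625; report counts there.

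**7.3.4, Test 2.** Make it two-sided to agree with 7.1.2, and report the number of distinct slides and readers behind the changes. Two-sidedness does not cure clustering: pooled two-sided error is still 19.5–21.3% at 60% switching. A sign-flip test in which all changes on one slide flip together is an optional sensitivity check. It held 0–4.4%, but with few changed slides it has little power (7% against 28% for the pooled two-sided test with 8 slides, 20% switching and AI right on 90% of them).

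**Cost.** Code and wording only, since reader and slide IDs are recorded (5.2.3). Data collection is complete and 10.3 reports no amendments, so the change is post hoc and must be reported as a departure. The statistical price is power with 10 units. No power figure is available for the reader-level test itself. As a guide, at a latent shift of 0.4 SD, slide ICC 0.10 and observed reader ICC about 0.05, the two-way robust test on direction has 95%, 87% and 68% power with 38%, 79% and 90% of scores unchanged in the absence of a shift. The pooled test has 99.9%, 99% and 95%, but not at a true 5% level.
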